#### Phenytoin arm

- Cardiovascular: Cardiac arrhythmia, circulatory shock;
- Central nervous system: phenytoin toxicity (nystagmus +/- unsteady gait +/- slurred speech +/- confusion). Drowsiness, suicidal ideation/tendencies;
- Dermatologic: Bullous dermatitis, skin rash;
- Gastrointestinal: Gingival hyperplasia;
- Genitourinary: Peyronie's disease;
- Hematologic: Macrocytosis, megaloblastic anaemia;
- Hepatic: Dupuytren's contracture, hepatitis ;
- Injection site reaction: Purple glove syndrome: oedema, discolouration and pain distal to injection site.

#### Levetiracetam arm

• Central nervous system: Behavioural problems including: aggression, agitation, anger, anxiety, apathy, depersonalisation, emotional lability, irritability, neurosis, psychotic symptoms, suicidal ideation/tendencies.

#### 12.1.2 Adverse reaction to an investigational medicinal product (AR)

All untoward and unintended responses to an investigational medicinal product related to any dose administered. All adverse events judged by either the reporting investigator or the sponsor as having a reasonable causal relationship to a medicinal product qualify as adverse reactions. The expression reasonable causal relationship means to convey in general that there is evidence or argument to suggest a causal relationship.

#### 12.1.3 Unexpected adverse reaction

An adverse reaction, the nature, or severity of which is not consistent with the applicable reference safety information (RSI)

When the outcome of the adverse reaction is not consistent with the applicable RSI this adverse reaction should be considered as unexpected.

The term "severe" is often used to describe the intensity (severity) of a specific event. This is not the same as "serious," which is based on participant /event outcome or action criteria.

#### 12.1.4 Serious adverse event or serious adverse reaction (SAE / SAR)

Any untoward medical occurrence that at any dose:

- results in death
- is life-threatening
- requires re-hospitalization or prolongation of existing inpatients' hospitalization, where it is not considered to be due to the initial trauma.
- results in persistent or significant disability or incapacity
- is a congenital anomaly or birth defect.

- is an important medical event - Some medical events may jeopardise the participant or may require an intervention to prevent one of the above characteristics/ consequences. Such events (hereinafter referred to as 'important medical events') should also be considered as 'serious'

Life-threatening in the definition of a serious adverse event or serious adverse reaction refers to an event in which the participant was at risk of death at the time of event; it does not refer to an event which hypothetically might have caused death if it were more severe.

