#### Secondary

- Compare outcomes between the two arms
  - extended Glasgow Outcome Scale
  - cognitive function
  - quality of life (EQ-5D-5L)
  - Liverpool Adverse Events Profile
- To compare adverse events between the two arms
- To compare the frequency of PTS between the two arms
- Undertake a detailed economic evaluation.

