# 12.1 Definitions

## 12.1.1 Adverse event (AE)

Any untoward medical occurrence in a participant or clinical trial participant administered a medicinal product and which does not necessarily have a causal relationship with this treatment.

An adverse event can therefore be any unfavourable and unintended sign (including an abnormal laboratory finding), symptom, or disease temporally associated with the use of an investigational medicinal product, whether or not considered related to the investigational medicinal product.

Please note: Recording of adverse events must start from the point of Informed Consent regardless of whether a participant has yet received a medicinal product.

However due to the pathology of traumatic brain injury, where the patients will be regularly monitored in the intensive care environment or on the neurosurgical wards, it is not practicable to record all adverse events. Therefore only adverse events of special interest (AESIs) will be recorded and **reportable** serious adverse events (SAEs) will be reported in accordance with this protocol. (Please see Section 12.1.4 for details of SAEs that are exempt from expedited reporting.)

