## 12.3 Expected Adverse Events/Serious Adverse Events (AE/SAE)

#### Expected SAEs exempt from expedited reporting

Due to the nature of traumatic brain injury, affected individuals can often develop surgical and medical complications. Expected systemic or surgical complications associated with TBI will not be reported as SAEs However, all SAEs (both reportable or non-reportable) will be captured on the study CRF (Case Report Form) or SAE recording log in the Investigator Site File, so that all serious adverse event data is captured.

In addition, any of the following systemic SAEs are also exempt from expedited reporting:

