#### 12.4 Evaluation of adverse events

The Sponsor expects that adverse events are recorded from the point of Informed Consent regardless of whether a participant has yet received a medicinal product. Individual adverse events should be evaluated by the investigator. This includes the evaluation of its seriousness, and any relationship between the investigational medicinal product(s) and/or concomitant therapy and the adverse event (causality).

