## 12.4.1 Assessment of seriousness

Seriousness is assessed against the criteria in section 12.1.4. This defines whether the event is an adverse event, serious adverse event or a serious adverse reaction

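### The SAE hospitalisation criterion in Section 12.1.4 contains an unblinded causal test, so some readmissions and prolonged stays can escape SAE review and any between-arm SAE count is open to attribution bias

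*Protocol*

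**What the plan says.** Section 12.1.4 lists the seriousness criteria. One of them counts a re-hospitalisation or a prolonged inpatient stay only "where it is not considered to be due to the initial trauma". None of the other criteria (death, threat to life, disability, congenital anomaly, important medical event) has an exception for trauma.

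Section 12.4.1 makes this list decisive: "Seriousness is assessed against the criteria in section 12.1.4". Section 12.4 says who applies it: "Individual adverse events should be evaluated by the investigator". Section 8.1 describes both trials as open label, and no blinded or independent assessment of events is described.

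Section 12.3 exempts expected complications of brain injury from expedited reporting, but still wants all SAEs on the CRF or the site's SAE log, "so that all serious adverse event data is captured". For events that are not serious, Section 12.1.1 narrows the recording: "Therefore only adverse events of special interest (AESIs) will be recorded".

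Sections 8.5.1 and 8.5.2 both list a comparison of adverse events as a secondary objective, separately from the Liverpool profile. For MAST-DURATION the wording is "To compare adverse events between the two arms". The matching outcome measures in Section 8.6.2 are adverse events of special interest (AESIs) during treatment and the Liverpool Adverse Events Profile. SAEs are not named there.

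**The concern.** Seriousness should describe what happened to the patient, and cause should be judged separately, as Section 12.4.2 does. Here a judgement of cause decides whether a hospitalisation is serious at all. If the site thinks the brain injury explains it, and no other criterion is met, the event never becomes an SAE.

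That matters more than usual in this trial because listed drug effects resemble the consequences of the injury. The phenytoin AESI list includes confusion, drowsiness and unsteady gait, and the levetiracetam list includes agitation, aggression and irritability. The investigator knows the allocation, and in MAST-DURATION the arms are meant to differ in drug exposure between 3 and 6 months. The same readmission could be put down to trauma more readily in one arm than in the other.

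Two things are at stake: the completeness of the central safety review, and the fairness of any between-arm count of SAEs. Section 16.3 gives this some weight. It justifies the 13% target effect in MAST-DURATION partly by the possibility of more side effects with a longer course.

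**Working it through.** The protocol states no figure on this point, so the main check is a comparison of sections.

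**1. Consistency of the definition.** Section 12.1.3 separates severe from serious and says that serious depends on the outcome of the event or the action taken. Section 12.1.4 adds a causal condition to one criterion only. By contrast, "results in persistent or significant disability or incapacity" stands without any condition on cause. The two sections do not agree.

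**2. Path of an excluded event.** Take an unplanned readmission, or a prolonged stay, that the site considers due to the trauma and that meets no other criterion.
- Section 12.4.1: it is not an SAE and not a serious adverse reaction, because both use the Section 12.1.4 list.
- Section 12 (introduction): the Chief Investigator's review, the six-monthly listing and the annual Development Safety Update Report draw on SAEs and on serious reactions. It is in none of them.
- Section 12.5: the Chief Investigator's assessment of relatedness and expectedness covers SAEs. It is not assessed.
- Section 12.3: the capture of all SAEs, reportable or not, works only on events that already satisfy Section 12.1.4. It does not bring the event back.
- Section 12.4.4 can be read as asking sites to log non-serious events, but Section 12.1.1 restricts recording to AESIs. Section 12 also does not require sites to report to the centre any event or reaction that is not a serious reaction.

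**3. Do AESIs fill the gap?** In part. They go on their own form whatever their seriousness. However, the lists are headed by drug arm, none is given for patients on no drug, and Section 8.6.2 limits the outcome to the treatment period. Section 6.1 names drowsiness as a side effect of levetiracetam, yet only the phenytoin list contains it. A levetiracetam patient readmitted with drowsiness that is attributed to trauma would be neither an AESI nor, without another criterion, an SAE.

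**4. Possible size, under assumptions.** The protocol gives neither a readmission rate nor a share attributed to trauma, so both are assumed here. Let R be the true rate of re-hospitalisation or prolonged stay, equal in both arms, and let s be the share attributed to trauma.

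Recorded rate: p = R × (1 − s). Spurious difference: d = R × (s_A − s_B).

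With n = 188 per arm (Section 16.3, MAST-DURATION), let p̄ = (p_A + p_B)/2, se₀ = √[2p̄(1 − p̄)/n] and se₁ = √[(p_A(1 − p_A) + p_B(1 − p_B))/n]. The chance of a significant difference at two-sided 5% is Φ((d − 1.96 se₀)/se₁) + Φ((−d − 1.96 se₀)/se₁).

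| R (assumed) | s_A v s_B (assumed) | Recorded p_A v p_B | Chance of a false significant difference |
|---|---|---|---|
| any of 10% to 40% | 50% v 50% | equal | 5% |
| 10% | 60% v 50% | 4% v 5% | 7.5% |
| 20% | 60% v 50% | 8% v 10% | 10.4% |
| 40% | 60% v 50% | 16% v 20% | 17.2% |
| 10% | 70% v 50% | 3% v 5% | 16.7% |
| 20% | 70% v 50% | 6% v 10% | 29.8% |
| 40% | 70% v 50% | 12% v 20% | 56.2% |

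Example: R = 20% with shares of 70% and 50% gives 0.20 × 0.30 = 6% and 0.20 × 0.50 = 10%, so d = 4 points. Swapping the shares reverses the sign. The range shows that a bias is possible; it does not estimate it.

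**The case against.** The strongest reply is that the named outcomes do not use this definition. AESIs and the Liverpool profile carry the adverse-event objective in Section 8.6.2, and neither passes through Section 12.1.4. A reader might infer that the planned adverse-event outcome is itself biased. The protocol does not support that. The bias reaches the objective only if SAEs are counted under it, which the protocol does not say and the SAP may settle.

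A reader might also take the all-cause SAE count to be the only safety comparison free of assessor opinion. That is not so either. Section 14.1.1 measures all-cause mortality to 24 months, the Liverpool profile is a questionnaire, and Section 16.6 proposes to extract hospital admissions from national records regardless of what the site thought.

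Further points hold. The other seriousness criteria are untouched. Under Section 12.4.2 a merely possible drug relation already makes an event an adverse reaction, so a careful investigator may hesitate to call such a readmission due to trauma. In MAST-PROPHYLAXIS treatment lasts 7 days and Section 11.3.2 expects few patients to leave hospital sooner, so most readmissions fall off drug in every arm. In MAST-DURATION treatment beyond 6 months depends on clinical need, so the contrast in exposure does not last 24 months. The trial is also openly risk-adapted (Sections 10.1 and 12).

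These points narrow the concern without removing it. Section 16.6 plans the extracted admissions for costing, and no section assigns them to the Chief Investigator's relatedness review or the six-monthly listing. Risk adaptation justifies fewer expedited reports, which Section 12.3 already provides without changing what counts as serious. The short exposure in MAST-PROPHYLAXIS also moves attention to prolongation of the index stay, which the same clause covers.

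**Conclusion.** The point holds as a defect of definition with a limited reach. Section 12.1.4 conflicts with Section 12.1.3 and undercuts the capture intended in Section 12.3. Re-hospitalisations and prolonged stays that meet no other criterion can miss central safety review because of a judgement made by an investigator who knows the allocation. Any between-arm comparison of SAE counts is therefore open to attribution bias.

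The size and direction of that bias are unknown. It is nil if the attributed shares are equal in the arms. In the assumed range above it runs from 1 to 8 percentage points in recorded rates. Those values rest wholly on assumed readmission rates and attribution shares.

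The primary outcomes, AESIs, the Liverpool profile, mortality, events serious on other grounds and the extracted hospital admissions are not affected. This is a worthwhile, low-cost improvement to safety oversight and does not threaten the trial's main conclusions.

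**What to change.** - In Section 12.1.4, delete the causal clause from the hospitalisation criterion. Confining it to the index admission would not be enough, because prolonged stays would remain subject to the same unblinded judgement.
- Record in the CRF, as an SAE, every unplanned re-hospitalisation and every prolongation of stay caused by an untoward event, with the attributed cause in a separate field.
- Move the exception for events due to the initial trauma to Section 12.3, as an exemption from expedited reporting only.
- State that any between-arm comparison of SAEs is made regardless of attribution.

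The cost is amendment wording and some extra CRF lines at sites. Events not judged drug-related would generate no additional expedited reports.

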#### 12.1.5 Suspected Unexpected Serious Adverse Reaction (SUSAR)

A serious adverse reaction, the nature and severity of which is not consistent with the information set out in the Reference Safety Information

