#### **Hepatobiliary**

- Pancreatitis
- Liver failure

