### 12.6 Reporting of Suspected Unexpected Serious Adverse Reactions (SUSARs)

All suspected adverse reactions related to an investigational medicinal product (the tested IMP and comparators) which occur in the concerned trial, and that are both unexpected and serious (SUSARs) are subject to expedited reporting. Please see section 12.1.6 for the Reference Safety Information to be used in this trial.

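### The SUSAR definition in 12.1.5 needs both nature and severity to be unexpected, whereas 12.1.3 needs only one of nature, severity or outcome; the two must be aligned, and the exemption in 12.3 needs an explicit causality condition

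*Protocol*

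**What the plan says.** The protocol gives two tests for an unexpected reaction.

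- Section 12.1.3 defines the unexpected adverse reaction as "An adverse reaction, the nature, or severity of which is not consistent with the applicable reference safety information (RSI"). It then adds a further route: "When the outcome of the adverse reaction is not consistent with the applicable RSI this adverse reaction should be considered as unexpected".
- Section 12.1.5 defines a SUSAR as "A serious adverse reaction, the nature and severity of which is not consistent with the information set out in the Reference Safety Information". It does not mention outcome.

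The reporting rule is in 12.6. It begins "All suspected adverse reactions related to an investigational medicinal product (the tested IMP and comparators) which occur in the concerned trial" and continues "and that are both unexpected and serious (SUSARs) are subject to expedited reporting". Sections 12.6.1 and 12.6.2 send such reports to the sponsor, the competent authority and the ethics committee, within 7 calendar days if fatal or life-threatening and within 15 otherwise.

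Section 12.3 first says that expected complications of TBI are not reported as SAEs. It then introduces a list of events by body system: "In addition, any of the following systemic SAEs are also exempt from expedited reporting". The list includes "Liver failure", pancreatitis, renal failure, coagulopathy and septicaemia. The sentence carries no condition on causality. In 12.1.1 the phenytoin events of special interest include "Hepatic: Dupuytren's contracture, hepatitis", so the protocol itself foresees a hepatic effect of the drug.

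**The concern.** The definition of a SUSAR decides which serious reactions reach the regulator and the ethics committee on a fixed clock. If two sections of one protocol give different tests, two investigators can classify the same event differently, each with a section to cite. The likely case is a reaction that the RSI lists but that occurs with a severity or outcome the RSI does not describe.

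The exemption in 12.3 raises a related, weaker question. It works by event term. An investigator who reads only that section could treat a listed event as exempt even when a trial drug is suspected. Section 12.5 does not settle the matter, because it requires onward notification to the sponsor only of reportable SAEs, and 12.1.1 ties that word to the exempt events.

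**Working it through.** No sample size, error rate or event count enters this point, so the check is a comparison of sections.

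**Step 1: apply both definitions to a serious reaction related to a trial drug.**

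| Departs from the RSI in | Unexpected under 12.1.3? | SUSAR under 12.1.5, read literally? |
|---|---|---|
| nothing | no | no |
| nature and severity | yes | yes |
| severity only | yes | no |
| nature only | yes | no |
| outcome only | yes | no |

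The first four rows cover every combination of nature and severity with outcome consistent; 2 of the 4 are classified differently. The outcome row is a third disagreement. The nature-only row should be almost empty in practice, since an RSI would not normally state a severity for a reaction it does not list. The rows that matter are severity only and outcome only.

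**Step 2: see whether 12.6 settles it.** Section 12.6 makes the trigger unexpected and serious, and item (c) of 12.6.3.1 repeats those two words together with a suspected causal link. The only definition of unexpected is in 12.1.3, so this route leads to the broader test. But 12.6 also attaches the label SUSAR to that trigger, and the only section headed as the definition of that label is 12.1.5. Section 12.6 thus invokes both tests at once. It favours 12.1.3 without removing the conflict.

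**Step 3: see what still happens to a reaction misclassified under 12.1.5.** It remains a serious adverse reaction. Section 12 requires serious adverse reactions to be recorded and reported to the sponsor, and 12.2 sends them to 12.5. What could be lost is the 7- or 15-day report to the regulator and ethics committee.

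**Step 4: apply the sections to an event on the 12.3 list that is judged possibly related.**

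- Section 12.4.2 makes a possible, probable or definite relationship an adverse reaction, and an unlikely or absent one an adverse event.
- Section 12.2, on reactions, sends serious ones to 12.5. Section 12.3 is headed as dealing with adverse events and SAEs.
- Section 12 waives sponsor reporting of SAEs only when they are not serious adverse reactions or SUSARs.
- Against this, 12.1.4 defines SAE and SAR together in one broad definition, 12.3 speaks of non-reportable SAEs that are captured on the CRF or a site log, and 12.5 limits onward notification to reportable SAEs.

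The first three provisions keep a related event reportable. The last leaves room to read it as exempt.

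**Step 5: follow the cross-references.** Section 12.1.1 points to 12.1.4 for the exempt SAEs, but the list is in 12.3. Sections 12.6.2.1 and 12.6.2.2 point to parties listed in 12.5.1, which does not exist; the parties are in 12.6.1.

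**The case against.** The strongest reply is that the protocol reaches the right result when read as a whole. The operative rule uses the word unexpected, which only 12.1.3 defines. Section 12.5 makes the chief investigator responsible for having every SAE assessed for relatedness and expectedness. Under 12.4.2 and 12.2, liver failure judged possibly due to phenytoin is a serious adverse reaction and not an exempt SAE. The 12.3 list also has an ordinary purpose: 12.5 asks sites to report SAEs within 24 hours and 12.4.4 sends SAEs to the sponsor, so the list spares them reports of common, unrelated complications of TBI.

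Most of this stands. A reader might infer that serious drug-related reactions will escape expedited reporting, or that the list was meant to cover related events. The documents do not support either: both require 12.1.5 or 12.3 to be applied in isolation, against sections 12, 12.2, 12.4.2 and 12.6.

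A reader might also measure the problem by exposure: two of three PROPHYLAXIS arms (2/3 × 1221 = 814 participants) and all 428 in DURATION. Those are planned numbers on trial drug, not numbers of affected reactions.

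The hepatic example is only an illustration. The list of events of special interest is not the RSI, which is section 4.8 of two product summaries that are not in the protocol. Nor would any wording in 12.3 help where a site wrongly judges a drug reaction to be a complication of the injury; that is an error of causality assessment.

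What the reply does not remove is the contradiction between 12.1.3 and 12.1.5, or the unclear use of reportable.

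**Conclusion.** The contradiction is real and should be corrected. On a literal reading, 12.1.5 excludes listed serious reactions of unexpected severity or outcome that 12.1.3 and 12.6 together make reportable. The consequence at stake is the 7- or 15-day report to the regulator and ethics committee; notification of the sponsor is preserved by section 12 and 12.2. The 12.3 point is secondary: the protocol does contain a causality rule, in 12.4.2 and 12.2, but 12.3 and 12.5 do not refer to it clearly.

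This is a drafting fault that permits misclassification. It is not evidence that any report has been or will be missed. Its frequency cannot be estimated from the document, which gives neither the content of the RSI nor expected rates of serious reactions. No endpoint, estimate or sample size is affected.

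**What to change.** 1. Reword 12.1.5 along these lines: *a serious adverse reaction that is unexpected as defined in 12.1.3, that is, whose nature, severity or outcome does not agree with the RSI*. Replacing and by or would not be enough, because outcome would still be missing.
2. State in 12.3 that the exemption covers only events assessed as unlikely or unrelated to the IMP, and that a listed event assessed as possibly, probably or definitely related is reported as a serious adverse reaction under 12.5 and, where unexpected, 12.6.
3. Correct the cross-references: 12.1.1 should point to 12.3, and 12.6.2.1 and 12.6.2.2 should point to 12.6.1.

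The cost is a few sentences in a protocol amendment and a note to sites. The downside is perhaps a few additional expedited reports.
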